3.4.3 Other Therapy

No other dental therapies are permitted in conjunction with the study treatments, dental emergencies excluded (i.e. Acute abscesses, Pulpitis, tumors or oral lesions).

3.4.4 Postsurgical Care

Patients will be instructed to take 500 mg of amoxicillin three times a day for 7 days, starting at least one hour prior the procedure. In case of allergy to amoxicillin, patient will assume 300mg Clindamycin three times a day for 7 days. Subjects will be advised to follow good oral hygiene habits in all non-study sites by brushing twice daily using a soft bristled toothbrush, and flossing once per day. All subjects will be instructed to avoid brushing and avoid the use of interdental cleaning devices for the first seven days following the surgical

procedure. In addition, all subjects will be instructed to avoid chewing directly on the test sites and to avoid trauma to the test sites for the first week following the surgery. During that interval, the subjects will be instructed to rinse twice daily after meals with 0.12% chlorhexidine gluconate non-alcohol oral rinse. After the first week, the subjects will be instructed to resume gentle tooth brushing and interdental cleaning with dental floss and continue the 0.12% chlorhexidine gluconate oral rinse for the first 4 weeks following surgery. All subjects will receive local implant cleaning at the month 3, 6 and 12 follow up visits.

3.4.5 Management of Post-Surgical Oral Pain

Any pre-surgical pain medications should be recorded and noted as such (i.e. pre-surgical pain medication). Post-surgical pain can be divided into mild, moderate, and severe levels and requires a subjective assessment by the periodontists based on knowledge of the surgical procedure performed and the presenting signs and symptoms of the subject. Pain as a secondary outcome to an adverse event, such as infection, is to be excluded if pain is an expected outcome of such events. Treatment of the pain is usually the best indicator of pain intensity.

MILD (Over-the Counter)

Acetaminophen 250 or 500 mg.

Products include: Tylenol®, Datrex®, Anacin®3

Ibuprofen

Products include: Motrin® 800 mg

MODERATE (Prescription Only)

Tylenol® No. 3 (codeine and acetaminophen)

Vicodin® (hydrocodone 5 mg and acetaminophen 500 mg)

Vicodin ES® (hydrocodone 7.5 mg and acetaminophen 750 mg)

Lortab® (hydrocodone 5 mg, 7.5 mg, 10 mg and acetaminophen 500 mg)

SEVERE (Prescription Only)

- Demerol® 50 mg (Meperidine)*
- Percocet® or Tylox® (oxycodone 5 mg and acetaminophen 500 mg)*

**Triplicate prescription where applicable*

3.4.6 Post-surgical Control, Professional Tooth Cleaning , Maintenance Care.

The objective of the post-operative appointments for professional tooth cleaning is both the removal of plaque and staining from the treated areas and the monitoring of the healing events. Post-surgical controls and professional tooth cleaning will be performed at 3, 6 and 12 months post-surgical. At these appointments, the conditions of the soft tissue at the treated sites will be evaluated. The overall level of oral hygiene will be evaluated and reinstruction will be given as needed at all visits.

Instructions on post-operative care will be repeated at each appointment. In particular, the following points should be covered during the first month: (1) continue chlorhexidine rinses

(from surgery to four weeks post-op); (2) resume gentle brushing; and (3) avoid vigorous chewing on, or trauma to, the treated areas.

At week 6, subjects will be instructed to gradually resume interproximal cleaning, as well as chewing, in the treated areas. All subjects will be maintained by full mouth professional prophylaxis and calculus removal once every three months, excluding surgical sites which will be maintained supragingivally.

All treatment-related adverse events that occur up to 30 days excepting surgery related AEs within 48 hours after any treatment will be recorded in CRFs, and all serious adverse events throughout the study will be recorded.

3.5 Clinical Assessments

3.5.1 Summary of Clinical Assessments

All examinations and measurements will be performed in accordance with the Schedule of Events.

Data will be collected and assessments will be made on study sites treated.

3.5.2 Primary Efficacy Assessment

- Esthetic satisfaction from baseline to 6 and 12 months of all treated areas, as assessed by both the examiner and the subject using the Visual Analog Scale (VAS), prior to and after viewing baseline photos
- Subject pain/discomfort questionnaire

- Change from baseline in probing depth
- Change from baseline visit in clinical attachment level
- Change from baseline visit in width of the keratinized tissue
- Change from baseline in radiographic a) bone gain; B) pathology

3.5.3 Probing Depths

Clinical probing depths of the periodontal sulcus will be measured using the a UNC 15 periodontal probe. Measurements will be performed without local anesthesia at six (6) locations around each study tooth. The number of additional locations to be measured around each experimental site will be determined by the extent and morphology of the area. Interproximal pocket depths will be recorded at the deepest point probable at the contact points from both buccal and lingual aspects. Buccal and lingual pocket depth measurements will be recorded at the mid-buccal and mid-lingual sites. All pocket depth measurements will be rounded down to the nearest mm and recorded. In conjunction with recording the pocket depths, any bleeding from the periodontal pockets will be indicated by marking an asterisk on the figure recorded for the depth measurement for that same pocket.

3.5.4 O'Leary Plaque Index

The plaque index is determined by scoring the percentage of individual tooth surfaces with plaque.

The following procedure will be followed:

Apply disclosing solution to all exposed tooth surfaces.

Rinse to remove any excess solution.

Examine each tooth surface (mesial, distal, facial, lingual) at the dento-gingival junction for presence of plaque.

[figure not shown]
Presence of plaque at the dento-gingival junction is indicated by making a dash in the appropriate spaces on the plaque control record diagram (see Figure 1).

If a tooth is missing, draw a line through the tooth on the diagram. Missing teeth should not be counted in the total number of surfaces scored.

Calculate the plaque index by dividing the number of surfaces with plaque by the total number of surfaces scored, and then multiply by 100 to obtain a percentage.

Figure 1 Plaque Control Record

3.5.5 Laboratory Assessments

The following laboratory assessments will be conducted at screening:

- Urine pregnancy test (females of child-bearing potential only)

CONFIDENTIAL AND PROPRIETARY INFORMATION OF Creighton University School of Dentistry Department of Periodontics

Protocol Number: CUSD2

Revision: October 22nd 2018

Original Issue Date: January 6th 2017

3.6 Schedule of Investigational Events

3.6.1 Screening Visit (Visit 1)

At the screening visit the following procedures and assessments will be performed within 32 days prior to surgery:

- Informed Consent
- Subject registration
- Medical history collection and physical examination:
 - Record of past therapy
 - Urine pregnancy test (females of child-bearing potential only)
 - Medications
- Dental history collection
 - Record of past therapy
- Screening assessments to determine eligibility:
 - O'Leary Plaque Index
 - Probing depths
 - Implant mobility,
 - Clinical attachment level
 - Obtain baseline radiographs of study sites
- Dental cleaning

- Oral hygiene instruction
- Supragingival plaque control, as appropriate
- Examiner and subject baseline esthetic satisfaction VAS assessments
- Radiographs of all target study sites

3.6.2 Baseline/Treatment (Visit 2)

Visit 2 may occur concurrently with Visit 1. If separate visits are to occur, Visit 2 must occur within 32 days of the screening examine.

- Examiner calibration (for first 2 subjects enrolled only)
- Preoperative and Intraoperative digital photographs
- Concomitant medications
- Surgical procedure
- Post-operative instructions
- Collection of any Adverse Events

3.6.3 Post op - Week 1 (Visit 3)

- An Investigator will rate and record the judgment of healing
- Study personnel will obtain clinical photographs of surgical sites taking care not to place apical tension on flap

- Post-operative instructions (e.g. Chlorhexidine rinse) and pain management according to standard procedures
- Complete Pain Rating Scale
- Rate and record color and texture of treated areas
- Adverse event review
- Concomitant medication review
- Suture removal according to healing
- Measurement of width of keratinized tissue
- Pain Medication review

3.6.4 Post op – 1 Month (Visit 4)

- Rate and record the color and texture of treated areas
- Digital photographs
- Rate and record judgment of healing
- Clinical attachment level
- The examiner and subject esthetic satisfaction VAS assessments (before and after viewing baseline photos)
- Supragingival plaque control as indicated
- Oral hygiene instruction
- Complete pain rating scale
- Concomitant medications

- Collection of Adverse Events
- Pain medication review

3.6.5 3-Months Follow up (Visit 5)

At the month 3 visit (Day 90 ± 14 days) the following procedures and assessments will be performed:

- Rate and record the color and texture of treated areas
- Digital photographs
- Rate and record judgment of healing
- Measurement of width of keratinized tissue
- Clinical attachment level
- The examiner and subject esthetic satisfaction VAS assessments (before and after viewing baseline photos)
- Supragingival plaque control as indicated
- Oral hygiene instruction
- Complete pain rating scale
- Concomitant medications
- Collection of Adverse Events
- Pain medication review
- Implant area professional cleaning

3.6.6 6 Months Follow up. (Visit 6)

Subjects will return to the clinic for a study visit 6 months (\pm 14 days) after surgery. The following procedures and assessments will be performed at this visit:

- Digital photographs
- Radiographs of all treated sites
- The examiner and subject esthetic satisfaction VAS assessments (before and after viewing baseline photos)
- Rate and record the color and texture of treated areas
- Rate and record judgment of healing
- Measurement of width of keratinized tissue
- Clinical attachment level
- Supragingival plaque control as indicated
- Oral hygiene instruction
- Complete pain rating scale
- Concomitant medications
- Probing depth
- Collection of Adverse Events
- Pain medication review
- Adverse Events review
- Implant area professional cleaning

3.6.7 12 Months Follow up. (Visit 7)

Subjects will return to the clinic for a study visit 6 months (\pm 14 days) after surgery. The following procedures and assessments will be performed at this visit:

- Digital photographs
- Radiographs of all treated sites
- The examiner and subject esthetic satisfaction VAS assessments (before and after viewing baseline photos)
- Rate and record the color and texture of treated areas
- Rate and record judgment of healing
- Measurement of width of keratinized tissue
- Clinical attachment level
- Supragingival plaque control as indicated
- Oral hygiene instruction
- Complete pain rating scale
- Concomitant medications
- Probing depth
- Collection of Adverse Events
- Pain medication review
- Adverse Events review
- Implant area professional cleaning

CONFIDENTIAL AND PROPRIETARY INFORMATION OF Creighton University School of Dentistry Department of Periodontics

Protocol Number: CUSD2
Revision: October 22nd 2018
Original Issue Date: January 6th 2017

3.7 Summary of Clinical Assessments (revised by UoC to meet assessment for implant tooth)

All examinations and measurements will be accomplished in accordance with the Schedule of Procedures (See Study Flowchart).

Oral Hygiene Status

Plaque recorded as present (1) or not present (0) on buccal and lingual surfaces of study teeth only

Bleeding following Angulated Probing

Bleeding will be registered at the surgical sites by means of pulling a probe with 60° angle to the root surface along the gingival margin.

Probing Pocket Depth

Distance of probe penetration (UNC 15 periodontal probe), measured from the gingival margin to the bottom of the probable pocket of the buccal surface to the nearest 0.5 mm.

Probing Proximal Pocket Depth

Distance of probe penetration (UNC 15 periodontal probe), measured from the gingival margin to the bottom of the probable pocket of the mesial and distal surface to the nearest 0.5 mm.

Clinical Attachment Level (CAL)

Distance of probe penetration (UNC 15 periodontal probe) measured from fixed reference point to the nearest 0.5 mm.

Proximal Probing Attachment Loss

Distance of probe penetration (UNC 15 periodontal probe) measured from fixed reference point at the mesial and distal aspect of the tooth to the nearest 0.5 mm.

Recession Depth

The distance between the fixed reference point and the soft tissue margin, measured to the nearest 0.5 mm with a UNC 15 periodontal probe. At the 6 and 12 month visit, tissue coronal to the fixed reference point will be recorded as a negative measurement

Width of Keratinized Tissue

The distance between the free gingival margin and the muco-gingival junction, measured to the nearest 0.5 mm with a graded periodontal probe. To facilitate the identification of the muco-gingival line, a probe may be used horizontally to move the mucosa in a coronal direction, creating a fold at the muco-gingival junction. Shiller's Iodine Solution may also be used to identify the muco-gingival junction

Examination of Defects During Surgery

After the flaps have been raised and the area debrided, characterization of the morphology and measurements of the defects are made, with the UNC 15 periodontal probe, and recorded as follows:

Alveolar Bone Level (Before and after osteoplasty if needed)

Notation of intra marrow penetration of alveolar crest

Notation of alveolar crest topography and whether osteoplasty was to be performed to refine contours.

Clinical Photographs

Clinical photographs will be taken of each tooth involved in the study before, during and after surgery, at Weeks 1, and 6 post surgery and at the 3, and 6 month follow-up examinations.

Post-Op Discomfort and Satisfaction Questionnaires

The subject's satisfaction with respect to postoperative discomfort between test and control quadrants will be evaluated by asking the subject about pain, bleeding, swelling and sensitivity using 10 cm visual analogue scale (See Appendix 1).

Procedure/ Assessment	Visit 1	Visit 2	Visit 3	Visit 4	Visit 5	Visit 6	Visit 7
	Screen 0-32 Days	Prior Surgery	Day 0	Post-op Day 7	1 Month 42± 7 Days	Month 3 90± 14 Days	Month 6 ±14 Days
Informed Consent	X						
Eligibility/ Study Lesion Identification, Subject Registration	X						
Demographics/Dental/Medical History	X						
O'Leary Plaque Index	X					X	X
Probing Depths	X					X	X
Pregnancy Test	X ¹						
Radiographic Exam	X					X	X
Dental Cleaning	X				X	X	X

CONFIDENTIAL AND PROPRIETARY INFORMATION OF Creighton University School of Dentistry Department of Periodontics

Protocol Number: CUSD2

Original Issue Date: January 6th 2017

Digital Photos		X	X	X	X	X	X
Examiner and Subject GORS and VAS of esthetic satisfaction		X	X	X	X	X	X
Plaque Control/Oral Hygiene Instruction	X	X	X	X	X	X	X
Concomitant Medications	X	X	X	X	X	X	X
Adverse Events		X	X	X	X	X	X
Clinical Attachment level	X					X	X
Examiner calibration		X					
Easy Graft Classic surgery		X					
Second stage surgery for submerged implants only						X	
Rate and record Judgment of Healing			X	X	X	X	X
Pain Rating Scale			X	X	X	X	X
Color and Texture			X	X	X	X	X
Width of Keratinized Tissue				X	X	X	X

1. In females of child-bearing potential only

CONFIDENTIAL AND PROPRIETARY INFORMATION OF Creighton University School of Dentistry Department of Periodontics

Protocol Number: CUSD2

Original Issue Date: January 6th 2017

Page 43 of 63

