	Assigning Relationship of Adverse Events to Treatment.....	48
	Serious Adverse Events	49
	Definition of a Serious Adverse Event.....	49
	SAE report to Sponsor and IRB	50
5.0	STATISTICAL AND ANALYTICAL PLAN	51
	Intent to Treat Population	51
	Safety Population	51
	Evaluable Population	51
	Missing Data	52
	Assessment of Safety	53
6.0	REGULATORY AND ADMINISTRATIVE REQUIREMENTS.....	53
6.1	IRB Requirements.....	53
6.2	Protocol Amendments	54
6.3	Informed Consent.....	55
APPENDIX I:	QUESTIONNAIRES/SURVEYS	56

PROTOCOL SYNOPSIS

Protocol Number	1015456
Title	A STUDY TO DETERMINE EFFICACY OF EASY GRAFT CLASSIC FOR THE TREATMENT OF PERI-IMPLANTITIS
Subject Population	Subjects with history of Moderate to Severe Peri-implantitis
Objectives	TO ASSESS THE EFFECTIVENESS OF EFFICACY OF EASY GRAFT CLASSIC
Number of Subjects	Maximum of 15 subjects
Number of Sites	Maximum 20 implants
Safety Endpoints	Assessments of subject safety will be based upon tabulations of the incidence of adverse events.
Efficacy Endpoints	
Stability and health of the attachment apparatus at 6 and 12 months by measuring:
 
 • Change from baseline in probing depth • Change from baseline in clinical attachment level • Change from baseline in width of the keratinized tissue • Change from baseline in radiographic A) bone regeneration ; B) pathology • Esthetic satisfaction from baseline to 12 months, as assessed by both the examiner and the subject using the Visual Analog Scale (VAS), prior to and after viewing baseline photos • Subject pain/discomfort questionnaire

CONFIDENTIAL AND PROPRIETARY INFORMATION OF Creighton University School of Dentistry Department of Periodontics

Protocol Number: CUSD2

Revision: October 22nd 2018

Original Issue Date: January 6th 2017

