Due to scarcity of literature on the use of alloplast on peri-implant treatment, the purpose of the study is to assess the effectiveness of the novel in-situ hardening β -TCP material, Easy-Graft[®] CLASSIC and polylactide based biodegradable membrane, GUIDOR[®] Biodegradable Matrix Barrier, following clinically adequate decontamination procedures. The author thinks that the specific properties of this grafting material may favor treatment of peri-implantitis. A recent study by Canullo¹⁶ et al. analyzed the efficacy of Easy-Graft[®] CLASSIC on the treatment of peri-implantitis. After removal of granulomatous tissue and decontamination of the titanium exposed implant surface, Easy-Graft was placed on the defect as a protection from soft tissue invasion. The authors noted a pronounced increase in mucosal recession and clinical attachment level with stable peri-implant conditions at six and 12 months. Plaque index, bleeding on probing and probing depths values were significantly reduced at six and 12 months. Radiographic analysis demonstrated from partial to complete filling of the defect in all of the cases at six and 12 months.

Easy-graft remains moldable until it comes in contact with blood or tissue fluids. When the material is soaked in blood in bone defects it hardens in a few minutes to form stable porous scaffold for bone regeneration. This characteristic of graft material gives better handling for the clinician. The hardening of the material could provide an increased stability of the blood clot around implant defect and favor hard tissue deposition and maturation. The Easy-Graft[®] CLASSIC manufacturer recommends GUIDOR[®] Bioabsorbable Membrane Matrix to be used

¹⁶ Canullo I, Peñarrocha Oltra D, Tallarico M, Aloy Prosper A, Chocer H, Peñarrocha Diago M. Surgical treatment of circumferential and semicircumferential defects due to periimplantitis: a prospective case series cohort study. J Oral Science Rehabilitation. 2016 Dec;2(4).

simultaneously in order to maximize its effects. The main difference between this proposed study and Canullo's will be the use of GUIDOR® Bioabsorbable Membrane Matrix in conjunction with Easy-Graft® CLASSIC

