The preliminary phase of the study will comprise completion of medical and dental histories, signing of consent forms, obtaining radiographs and photographs, performing screening assessments to confirm eligibility, and instruction in oral hygiene techniques. Before the periodontal surgical procedure, subjects may undergo plaque removal, then root planing and scaling to the areas to be treated, if such treatment is indicated. The final esthetic outcome of the treated sites will be evaluated by the patients using the Visual Analog Scale (VAS) ranging from "Very Unsatisfied" to "Very Satisfied" (before and after viewing baseline photos). Other clinical assessments will include: subject pain/discomfort questionnaire, change in probing depth, change in clinical attachment level, change in width of keratinized tissue from baseline to 6 and 12 months and change in radiographic bone gain and pathology. Digital photographs will be obtained at each study visit and radiographs of the test sites will be made at the baseline, 6 and 12 month visits.

The primary efficacy parameters will include:

- Esthetic satisfaction from baseline to six months of all treated areas, as assessed by both the examiner and the subject using the Visual Analog Scale (VAS), prior to and after viewing baseline photos
- Subject pain/discomfort questionnaire
- Change from baseline in probing depth (PD) measured from the mucosal margin to the bottom of the probeable pocket

- Gingival recession (Rec) measured from the implant platform (IP) to the mucosal margin
- Change from baseline visit in clinical attachment level (CAL) measured from IP to the bottom of the probeable pocket
- Change from baseline in width of the keratinized tissue (KT)
- Change from baseline in radiographic a) bone gain; b) pathology

INVESTIGATIONAL DEVICE

GUIDOR® easy-graft® CLASSIC

GUIDOR® easy-graft® CLASSIC is bone grafting system contains: syringe containing betatricalcium phosphate (β -TCP) granules coated with poly (lactide-co-glycolide) (PLGA) and ampule containing BioLinker® Activator (N-methyl-2-pyrrolidone and water).

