3.0 STUDY DESIGN

3.1 Overall Study Design

This study will be case series, with two periodontists and an examiner. Both of the periodontists will perform surgical procedures and record surgical measurements. The blinded examiner will perform all other clinical assessments. 15 subjects will be enrolled. Written informed consent will be obtained from each subject prior to any study related procedures.

The study will follow subjects for safety and efficacy for 6 and 12 months after their surgical treatment.

Screening will take place no more than 32 days prior to the first treatment and will include the clinical assessments required to confirm eligibility. Clinical photograph, radiographs of the implant treated, clinical measurements will be taken and recorded (Pocked Depth, Mucosal Recession, Clinical Attachment Level). Two to four (2-4) weeks prior to the first study treatment, subjects may undergo plaque removal and root planing and scaling to the areas to be treated, if appropriate. Also, they will receive personalized oral hygiene instructions to reach full-mouth plaque score (FMPS) <20% and full-mouth bleeding score (FMBS) <20%, which will be considered requirement for surgery to occur.

The day of surgery will be designated as Day 0. Subjects will have peri-implant regeneration surgery.

If possible, implant crown will be removed with attention not to damage it. Healing screw will be placed on the implants. Upon flap elevation and debridement of the peri implant lesion, the operator will record the type of bony defect associated to the treated implant (see Inclusion criteria 3). Titanium Implant surface will be debrided with rotating burs and brushes (PERI-SET Swden&Martina Inc.), and decontaminated with EDTA gel (Straumann® PrefGel. pH neutral, 24% EDTA) for 2 minutes and with the alternation of Perio-Flow Chlorhexidine mouthwash (GUM® ParoEx®, Chlorhexidine Gluconate Oral Rinse USP 0,12%, SUNSTAR) saline water and H₂O₂ using cotton pellets. After the completion of these procedures, Easy-graft® CLASSIC will be placed to fill the peri-implant defect.

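### The negative-value rule for recession covers only the 6 and 12 month visits, so change from a screening margin that lies coronal to the implant platform may come out too favourable or with the wrong sign

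*Combined protocol and SAP*

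**What the plan says.** Under Recession Depth, section 3.7 (Summary of Clinical Assessments) gives this definition: "The distance between the fixed reference point and the soft tissue margin, measured to the nearest 0.5 mm". A distance has no sign. The next sentence supplies one, but for two visits only: "At the 6 and 12 month visit, tissue coronal to the fixed reference point will be recorded as a negative measurement".

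Recession is also taken before surgery. Section 3.1 says of screening that "clinical measurements will be taken and recorded (Pocked Depth, Mucosal Recession, Clinical Attachment Level", and section 3.4.2 repeats this. No section gives a sign rule for that measurement.

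Section 2.0 names the landmark and lists the variable among the primary efficacy parameters: "Gingival recession (Rec) measured from the implant platform (IP) to the mucosal margin". Unlike the PD, CAL, keratinized tissue and radiographic items in the same list, this item is not worded as a change from baseline. The synopsis and sections 3.2.1 and 3.5.2 omit recession, and so do the visit lists in section 3.6 and the flowchart. Section 3.7 speaks of a fixed reference point without saying that it is the implant platform.

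**The concern.** A change score needs the same scale at both ends. If follow-up values are signed and screening values are not, then for any implant whose margin starts coronal to the platform the difference is not the movement of the margin. The error always runs towards apparent coronal gain, so it favours the treatment.

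The starting condition is not ruled out. The implant criteria in section 3.3.1 require a PD of at least 6 mm and bone loss above 25% of implant length. They do not require baseline recession, and no exclusion criterion concerns margin position.

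The direction matters because section 1.0 reports of an earlier series with this graft that "The authors noted a pronounced increase in mucosal recession and clinical attachment level". Recession is therefore a foreseeable unfavourable result, although that series did not use the membrane added here. The synopsis sets "Maximum 20 implants" and there is no control arm, so a few mis-signed sites could move the mean. The calibration in section 3.3.3 uses recession depth with a 1 mm tolerance, but agreement on magnitude would not reveal a shared sign problem.

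**Working it through.** The plan states no expected change in recession, power or sample size calculation, so there is no figure of its own to reproduce. The check is direct arithmetic.

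**Inputs.** From the documents: the visit-limited sign rule and 0.5 mm scale (section 3.7), recession taken at screening (sections 3.1 and 3.4.2), the platform as landmark (section 2.0), and at most 20 implants (synopsis). Assumed, because the documents do not give it: the screening margin lies a mm coronal to the platform, with a from 1 to 3 mm.

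**Formulas.** Positive values mean recession. The true signed baseline is -a, and f is the signed follow-up value.

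- True change = f - (-a) = f + a.
- Baseline entered unsigned as +a: recorded change = f - a, an error of -2a.
- Baseline entered as 0: recorded change = f, an error of -a.

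**Size per site.** For a = 1, 2 and 3 mm the unsigned error is -2, -4 and -6 mm, and the zero-entry error is -1, -2 and -3 mm.

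**When the sign is wrong.** With an unsigned entry, true recession (f + a > 0) is recorded as gain (f - a < 0) whenever -a < f < a, that is, when true recession lies between 0 and 2a. On the 0.5 mm scale this is 0.5 to 1.5 mm for a = 1, 0.5 to 3.5 mm for a = 2 and 0.5 to 5.5 mm for a = 3. With a zero entry the sign is wrong only when -a < f < 0.

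**Examples with a = 2 mm.**

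| f (mm) | True change | Unsigned baseline | Zero baseline |
|---|---|---|---|
| -1 | +1 | -3 | -1 |
| 0 | +2 | -2 | 0 |
| +1 | +3 | -1 | +1 |

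**Group illustration (assumed).** Take 20 implants that all truly recede by 1 mm. Some start 2 mm coronal and the rest 1 mm apical. A coronal starter (true -2 to -1) is recorded as -3 with an unsigned baseline or -1 with a zero baseline. The others are recorded correctly as +1. The true mean is +1.0 mm.

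| Share starting coronal | Mean, unsigned | Mean, zero |
|---|---|---|
| 0% | +1.0 | +1.0 |
| 25% | (5 × -3 + 15 × 1)/20 = 0.0 | (5 × -1 + 15 × 1)/20 = +0.5 |
| 50% | (10 × -3 + 10 × 1)/20 = -1.0 | (10 × -1 + 10 × 1)/20 = 0.0 |
| 100% | -3.0 | -1.0 |

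**Can the sign be recovered?** Section 2.0 defines CAL as follows: "Change from baseline visit in clinical attachment level (CAL) measured from IP to the bottom of the probeable pocket". Signed recession should therefore equal CAL - PD, and both are taken at screening. The limit is rounding. Section 3.5.3 says "All pocket depth measurements will be rounded down to the nearest mm and recorded", while section 3.7 records PD to 0.5 mm. A simulation with CAL to 0.5 mm, an assumed PD uniform on 6 to 10 mm and no probing error gave these results:

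| a (mm) | Negative sign recovered, PD rounded down to 1 mm | Negative sign recovered, PD to nearest 0.5 mm |
|---|---|---|
| 0.5 | about 25% | 100% |
| 1 | about 75% | 100% |
| 2 or 3 | 100% | 100% |

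**After the fix.** With one signed convention the recorded change is f + a in every row above, which is the true change.

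**The case against.** The strongest reply is that the plan is silent on the baseline sign, and silence is not an instruction. A sensible examiner may well sign the screening value too. The later visits may be named simply because submerged implants stay covered until they are reopened at 6 months (section 3.4.2). That explanation is an inference, but it does not imply a different scale at baseline. All of this stands. A reader might infer that the plan orders an unsigned or zero entry at screening, and it does not. The zero entry does not even follow from the definition, since a margin 2 mm from the landmark is not at distance zero. It is shown only as another way in which a site might fill the field.

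A reader might also infer that attachment gain is inflated. The documents do not support that: sections 2.0 and 3.7 both define CAL as a direct measurement from the reference point, and nothing derives it as PD plus recession.

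Nor is recession established as a formal primary endpoint. Its only support is the list in section 2.0, and section 5.0 plans no test or estimate for it.

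Finally, the sign can often be rebuilt from CAL and PD, reliably so at larger offsets, where the bias is largest. This stands in part. The plan specifies no such check, its PD rounding rules conflict, and the recovery rates above ignore probing error.

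What the reply does not remove is that the sign rule is limited to named visits while the same variable is recorded at another visit under a plain distance definition.

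**Conclusion.** The concern holds as a gap in a measurement definition. Followed literally, section 3.7 allows screening and follow-up recession to be on different scales wherever the margin starts coronal to the platform. The change can then be overstated in the favourable direction or reversed in sign.

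The size rests entirely on an assumed baseline position and an assumed share of affected implants. It is nil if every margin starts at or apical to the platform, or if examiners already sign the screening value.

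The reach is limited to recession itself, a parameter that section 2.0 calls primary but the formal endpoint and assessment sections leave out. Severity is minor to moderate. The study's other conclusions do not depend on it.

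**What to change.** In section 3.7, replace the visit-limited sentence with a rule along these lines: at every visit at which recession is recorded, including screening/baseline, a soft-tissue margin coronal to the implant platform is entered as a negative value. In the same entry:

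- name the implant platform as the fixed reference point, to agree with section 2.0;
- define change in recession as follow-up minus baseline, so that positive means recession;
- compare the sign of recorded recession with CAL minus PD at each visit where all three are recorded, and query disagreements rather than overwrite them.

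The check works best if sections 3.5.3 and 3.7 are first reconciled to one PD rounding rule. In the simulation, rounding PD down made CAL minus PD up to 1 mm too high.

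The cost is a sentence or two of protocol text, a signed field on the baseline case report form and a simple data query. No new measurement is needed. If screening values already exist, review them with the same check and report how many signs could not be confirmed. While editing, the sponsor should also say whether recession is an endpoint and, if so, add it to sections 3.2.1 and 3.5.2, the visit lists and the flowchart.
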